## 9.6 Data Management

The survey will be conducted according to the Standard Operating Procedures (SOPs) of IQVIA Primary Intelligence and IQVIA Real World Evidence Solutions.

As the questionnaire is simple and short a single data entry will be sufficient. Collected data will be entered and stored in a database specific to the survey and the country. A study database will be created by merging of databases of each country.

Data will be checked in terms of consistency before data analysis:

- Removal of duplicates (if required);
- Data labelling and data formatting;
- Range and consistency checks for each variable to identify potential non- admissible values;
- Cross-check the consistency of data for related variables (if feasible);

The study database will be locked once validated.

#### 9.6.1 Data Entry/Electronic Data Capture

The data will be self-entered by the participating prescriber, pharmacist, or patient.

The survey will be conducted according to the SOPs of IQVIA Primary Intelligence and IQVIA Real World Evidence Solutions. Data will be collected using an EDC system (Merphin) developed following a full validation process. A rigorous System Development Life Cycle is used for validation that complies with internal IT SOPs of Primary Intelligence (IQVIA).

Template No.: RWI\_TP\_EPI0016 Revision 1 Reference: RWI\_WI\_EPI0005

Protocol/Study No: SC02 EMA/2018/19/PE

Page 43 of 92

Unit testing and formal validation will occur on all appropriate systems and components during the build stage. The internet-based repository will be used to store survey data and other relevant programme information. Questions are programmed to ensure that they are asked in the appropriate sequence. Skip patterns are clearly indicated. Respondents cannot go back to a question once the question has been answered and cannot skip ahead without answering the previous question. Programming will be reviewed by Quality Control and simulated users (User Testing) prior to implementation.

#### 9.6.2 Source Documents

Not applicable.

## 9.6.3 File Retention and Archiving

The study documentation will be archived internally at IQVIA. The web questionnaires data will be stored on the survey database for 12 months.

Data storage will be in line with national data protection requirements for each of the countries where the study will be conducted.

All other documentation pertaining to the study, including paper and electronic records will be retained for a minimum of 5 years after the end of the study, in accordance with IQVIA SOPs.

## 9.7 Data Analyses

The statistical analyses will be described and further detailed into a Statistical Analysis Plan (SAP). The described analysis below might be revised, and adjustments might occur. The final SAP version will include (empty) table shells to be populated for the clinical study report.

#### 9.7.1 General Considerations

The statistical analysis will be conducted using the Statistical Analysis Software (SAS®) software V9.4 or above on WindowsTM (SAS Institute, North Carolina, USA).

Continuous variables will be described by their number (of valid cases and missing values), mean, standard deviation, and median, Q1, Q3, minimum and maximum. Categorical variables will be described as the total number and relative percentage per category. These will be the percentage per category. In case of multiple-choice questions, the frequency of each option provided by the prescribers, pharmacists, and patients will be reported in the statistical results. Different combinations of the answers provided will not be considered. Confidence intervals of 95% will be evaluated, when relevant. Variables with free text options will be analysed by text mining method to extract and identify meaningful

Template No.: RWI\_TP\_EPI0016 Revision 1 Reference: RWI\_WI\_EPI0005

Protocol/Study No: SC02 EMA/2018/19/PE

Page 44 of 92

information. Detailed information on the approach for deriving keywords for text mining will be described in the SAP.

The proportions of correct and appropriate answers to selected questions asked in the questionnaire will be expressed among prescribers, pharmacists, and patients who provided answers to those questions (the missing data will not be counted as a denominator in proportions). The endpoint will be assessed overall, by country for the 3 surveys. In a first step, calculations will be performed on raw data. No projection factor will be applied to generalise the results to the entire participants' universe. Consequently, the line "Overall - unweighted results" will show only the results observed on the overall sample and will not reflect the countries' universe since this sample is not proportional to the size of the lists in each country. In a second step, the results will be weighted according to the real proportion of prescribers, pharmacists, and patients in each country in order to accurately reflect the population that the survey seeks to measure.

## 9.7.2 Planned Analyses

## 9.7.2.1 Analysis of Participation Rate

The following different cases of total responses and non-responses will be distinguished and analysed for prescribers, pharmacists and patients:

- Prescribers, pharmacists or patients who did not participate (R): Prescribers, pharmacists or patients who did not respond or that explicitly indicated their refusal to participate (if available)
- Prescribers, pharmacists or patients with partially answered questionnaires (P): Prescribers, pharmacists or patients who clicked on the link provided in the invitation email, and who began answering the questionnaire but never submitted it
- Prescribers, pharmacists or patients with completed questionnaire (C): Prescribers, pharmacists or patients who completed the entire questionnaire
- Contacted prescribers, pharmacists or patients: Prescribers, pharmacists or patients who were reached by phone or who received a web link to the online survey via email OR patients who received a web link to the online survey via email = C+P+R
- Prescribers, pharmacists or patients who agreed to participate: Prescribers, pharmacists or patients who participated in the survey (e.g.by clicking on the link provided in the invitation email) = P+C
- The prescribers', pharmacists' and patients' participation in the survey were examined as follows:
  - $\circ$  Response rate = C/(C+P+R)
  - $\circ$  Refusal rate = R/(C+P+R)

Template No.: RWI\_TP\_EPI0016 Revision 1 Reference: RWI\_WI\_EPI0005

Protocol/Study No: SC02 EMA/2018/19/PE Page 45 of 92

The participation rates will be presented by country.

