#### **Population:**

The following criteria will be checked at the beginning of the web questionnaire:

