#### 9.2.1 Participant selection

#### 9.2.1.1 Prescriber Selection

Choice of the specialties to include in the survey will be based on the specialties that have been targeted for distribution of the DHPC and educational material (EM) by the relevant national competent authorities in the selected countries, for e.g. specialists including GPs, internists, rheumatologists, dermatologists, gastroenterologists etc. The choice of specialties can be variable between countries. To the extent possible, prescribing patterns will be obtained from IQVIA data assets as supportive evidence to document the choice of specialties. Please refer to Annex 2. List of Healthcare Professionals for a complete list of prescribers who received the DHPC/EMs per country.

In the absence of comprehensive lists of MTX prescribers, the initial sampling frame for the identification of participating prescribers will be based on the list of all prescribers (OneKey, IQVIA, OneKey is an IQVIA managed database with information of health care professionals) in each of the relevant specialties in the targeted country. OneKey databases are constructed and updated through manual and automated means from various sources, including publicly available sources. OneKey is the most comprehensive list of HCPs in the

Template No.: RWI\_TP\_EPI0016 Revision 1 Reference: RWI\_WI\_EPI0005

Protocol/Study No: SC02 EMA/2018/19/PE

Page 28 of 92

world with very high coverage in most countries (33). Also, in EU PAS Register, it can be seen where OneKey database has been used for other post-authorisation safety studies (PASS) such as EUPAS34465 and EUPAS32142.

Since the study objective is to determine the extent of prescriber awareness and knowledge of the risk of inadvertent overdose due to daily instead of weekly use of MTX, only prescribers who have prescribed in indications requiring once-weekly MTX (in the past 3 months) will be selected. As this information is not available in the lists of prescribers, the survey will be preceded by a set of questions to check the eligibility of prescribers. Among these, it will be asked if the prescriber has prescribed in indications requiring once-weekly MTX in the past 3 months. If the answer is no, the survey will not be administered to that prescriber.

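### The participation formulas have no class for people screened out as ineligible, so the by-country response and refusal rates mix ineligibility with non-response

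*Protocol*

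**What the plan says.** Section 9.7.2.1 defines three classes.

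- R is people "who did not respond or that explicitly indicated their refusal to participate (if available").
- P is people who opened the link "and who began answering the questionnaire but never submitted it".
- C is "Prescribers, pharmacists or patients who completed the entire questionnaire".

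Contacted people are those reached by phone or sent the link, a definition ending with "patients who received a web link to the online survey via email = C+P+R". The three classes are therefore meant to cover everyone contacted. People who agreed to participate are those "who participated in the survey (e.g.by clicking on the link provided in the invitation email) = P+C". The response rate is C/(C+P+R) and the refusal rate is R/(C+P+R). Participation rates are presented by country.

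On eligibility, the Abstract (Population) says: "The following criteria will be checked at the beginning of the web questionnaire". Sections 9.4.1 and 9.4.3 also place the eligibility or screening questions within the questionnaire. Section 9.2.1.1 puts a set of eligibility questions ahead of the survey for prescribers and adds: "If the answer is no, the survey will not be administered to that prescriber". The same section says that the sampling frame is all prescribers in the relevant specialties, because comprehensive lists of methotrexate prescribers do not exist. Section 9.4.1 also puts consent at the start of the questionnaire, and section 9.2.3 makes lack of consent an exclusion criterion.

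**The concern.** A person who opens the link, answers the eligibility questions and is turned away has responded, has not refused and cannot complete. None of the three classes was written for that person, yet the protocol states that the three classes add up to everyone contacted.

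Screen-outs are to be expected, above all among prescribers, whose list carries no information on methotrexate prescribing. They may also differ by country: Annex 2 lists general practitioners among the recipients of the materials in Germany, France, Greece and Poland, but not in Sweden. A difference in response rate between countries could then reflect who was on the list rather than who was willing to answer.

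These rates matter because section 9.9.1 accepts selection bias as a limitation and says that, for pharmacists and patients, the vendor collects no personal data on non-respondents. For prescribers, the same section plans to compare participants with non-participants. If participation there means P+C, ineligible prescribers would enter the participant side.

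Consent decliners raise a smaller problem. They belong in R as explicit refusers, but they have already opened the link and so also match the example given for agreement.

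**Working it through.** **Do the classes cover everyone?** Take a prescriber who opens the link and reports no weekly methotrexate prescribing in the past 3 months.

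- C: no, because the survey is not administered.
- R: no, because the person neither failed to respond nor refused.
- P: yes, if the eligibility questions are part of the questionnaire (Abstract, 9.4.1, 9.4.3). If they come before it (9.2.1.1), the person never began and fits no class.

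If P, the person also counts as having agreed to participate. If no class, the statement that contacted people equal C+P+R fails. The person was contacted in both cases, so remains in the denominator that the protocol equates with everyone contacted.

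**Effect on the rates.** The protocol states no response-rate figure, so there is nothing to reproduce. Let N be the number contacted and S the number screened out. With S absorbed into P, the drafted response rate is C/N whatever S is, so it cannot separate ineligibility from non-response.

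**Illustration.** C = 150 is the target in section 9.5.1. All other counts are assumed: N = 3,000, true break-offs P = 50, no over-quota exclusions, and S = 200 or 400. Then R = N − C − P − S, which is 2,600 or 2,400. The share eligible among those screened is e = (C+P)/(C+P+S), which is 200/400 = 0.50 or 200/600 = 1/3.

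| Figure | S = 200 | S = 400 |
|---|---|---|
| Response rate as drafted, C/N | 150/3,000 = 5.0% | 150/3,000 = 5.0% |
| Known screen-outs removed, C/(N−S) | 150/2,800 = 5.4% | 150/2,600 = 5.8% |
| Eligibility-adjusted, C/(C+P+e·R) | 150/(200+1,300) = 10.0% | 150/(200+800) = 15.0% |
| Agreed, with S in P, (C+P+S)/N | 400/3,000 = 13.3% | 600/3,000 = 20.0% |
| Agreed, S removed, (C+P)/(N−S) | 200/2,800 = 7.1% | 200/2,600 = 7.7% |
| Refusal rate as drafted, R/N | 2,600/3,000 = 86.7% | 2,400/3,000 = 80.0% |
| Refusal rate, S removed, R/(N−S) | 2,600/2,800 = 92.9% | 2,400/2,600 = 92.3% |

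The eligibility-adjusted row assumes that people who never opened the link are eligible at the same rate as those screened. The row that removes only known screen-outs does not need that assumption.

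**Sensitivity to the assumed counts.** With N = 1,500, C = 150, P = 20 and S from 50 to 600, the drafted response rate is 10.0% throughout. Removing known screen-outs gives 10.3% to 16.7%, and the eligibility-adjusted rate runs from 12.9% to 45.3%.

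**The case against.** The strongest defence is that C/(C+P+R) is a legitimate crude rate of completes per person contacted, and that section 9.7 leaves detail and revision to the statistical analysis plan. The protocol also has other sources on recruitment. Numbers eligible and response rates are monitored (9.2.4.1 to 9.2.4.3), screening logs are kept for pharmacists and patients (9.2.4.2, 9.2.4.3), and a separate recruitment report is planned (9.3.2). This much stands: the information is largely collected, and a crude rate is worth reporting. But none of these counts enters the formulas, and section 9.7.2.1 already fixes classes that an analysis plan would inherit.

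A second defence is that pharmacists and patients receive the link only after agreeing to take part (9.2.4.2, 9.2.4.3), so calling them agreed before the consent page follows the documented sequence. That is fair, and it limits the complaint about the agreement label mainly to prescribers, whose invitation email carries the link. It does not change the denominators.

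Some stronger readings are tempting but not supported:

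- A reader might infer that consent decliners have no class. They do, because R covers explicit refusal. Their problem is overlap with the click example.
- A reader might infer that screen-outs are partials by definition. That is the natural reading, but section 9.2.1.1 allows the other one.
- A reader might conclude that the true response rate is two or three times the reported one. That depends on invented counts and on an untested assumption about silent non-responders.

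**Conclusion.** The point holds. The protocol equates contacted people with C+P+R while its own screening step produces people who are in none of these classes, or in P only by default. The response and refusal rates therefore combine ineligibility with non-response, and comparisons between countries can be distorted where eligibility differs.

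The size cannot be known from the protocol. Under the 3,000-contact illustration, a drafted 5.0% becomes 5.4% or 5.8% with known screen-outs removed, and 10.0% or 15.0% only under the added assumption about non-responders.

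The damage is confined to the participation, agreement and refusal figures and to any judgement of non-response built on them. The awareness, knowledge and self-declared behaviour endpoints, the 80% success thresholds and the sample size rest on completed questionnaires and do not change. The fix is worth making because the rule, followed as written, gives a misleading figure and is cheap to correct.

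**What to change.** Amend section 9.7.2.1 as follows.

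1. Add a class S for people screened out as ineligible. If quotas are used (section 9.2.4 makes them optional), add a separate class Q for people turned away because a quota was full. Q must not be merged with S where over-quota people have passed the eligibility questions.
2. Restrict P to eligible, consenting respondents who break off.
3. State that consent decliners are in R, and remove clicking the link as the example of agreement.
4. Set contacted = C+P+R+S+Q, and report S and Q by survey and country.
5. Beside the crude rate C/contacted, report the response rate with known screen-outs removed from the denominator, C/(C+P+R+Q).
6. As a labelled sensitivity figure, report an eligibility-adjusted rate, C/(C+P+Q+e·R), with e = (C+P+Q)/(C+P+Q+S) if over-quota people have passed the eligibility questions. State the assumption that non-responders are eligible at the same rate as those screened.

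The cost is a wording change and slightly more reporting. Screen-out counts must be kept for prescribers, for whom section 9.2.4.1 mentions monitoring of eligible numbers but no screening log.

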## 9.7.2.2 Questionnaire Analysis

The statistical results of the selected countries will be presented in the same report, overall, per country.

The general statistical considerations described above (Section 9.7.1) will be applied for quantitative and qualitative variables. The numbers of missing data will be indicated. Missing values are expected to be few and distributed at random. Since there is no applicable method unanimously accepted, there will be no replacement or imputation of missing data (42). Confidence intervals of 95% will be evaluated for endpoint variables.

Analysis for the survey will be performed for patients, prescribers, and pharmacists separately for the endpoints described below:

- Awareness will be assessed through the percentage of
  - prescribers who receive and/or are aware of the DHPC, HCP guide, HCP checklist and patient card
  - pharmacists who are aware of the patient card and visual reminder on the outer packaging
  - o patients who receive and/or are aware of the patient card, the boxed warning in the packaging leaflet, and visual reminder on the outer packaging
- A **knowledge** score will be created to summarise all responses at individual prescriber, pharmacist, and patient level. An individual prescriber/pharmacist/patient score is calculated as the proportion of correct responses among all questions related to knowledge
- A **self-declared behaviour** score will be created (for prescribers and pharmacists) to summarise all responses at individual physician level. An individual prescriber/ pharmacist score is calculated as the proportion of desriable responses among all questions related to self-declared behaviour.

The number and relative percentage of prescribers/pharmacists/patients who have provided correct answer to each of the questions and then number and relative percentage of prescribers/pharmacists/patients with correct responses to 70%, 80%, 90% and 100% of all the questions will be described.

## Assessment of success

In each of the 3 surveys, the proportion of correct or desirable responses across all questions related to the evaluation of the objectives of the surveys will be considered to assess the success.

Template No.: RWI\_TP\_EPI0016 Revision 1 Reference: RWI\_WI\_EPI0005

Protocol/Study No: SC02 EMA/2018/19/PE

Page 46 of 92

The questions considered as complementary will not be included in the assessment of success. The details of the assessment of the success for each survey and each objective is described in Annex 5.

Success at the prescriber, pharmacist, patient level will be defined for each objective based on the number of sub-questions related to that objective being answered correctly or desirably. It is proposed to set the threshold to at least 80% of knowledge questions, including sub-questions, are completed with correct/desirable answers. .

A threshold of 80% successful prescribers/pharmacists/patients on each of the outcomes of awareness, knowledge and self-declared behaviour (self-declared behaviour is not for patients) would be considered appropriate for assessing the effectiveness of RMM.

If additional information from published literature becomes available at the time of reporting, then the results will be discussed in the context of this new information. The methods of reporting and analysis of results obtained will be done as already described in the Protocol and will be further detailed in the SAP.

## Profile of prescribers/pharmacists with incorrect answers

The profile of prescribers/pharmacists with incorrect answers to questions related to the main objectives (awareness, knowledge, and self-declared behaviour) will be described using all available and relevant prescribers'/pharmacists' characteristics collected in the survey (i.e., country, specialty, duration of practice, practice setting, prescribing/dispensing volume, age and gender).

## Profile of patients with incorrect answers

The profile of patients with incorrect answers to questions related to the main objectives (awareness and knowledge) will be described using all available and relevant patient characteristics collected in the survey (i.e., country, age range, indication).

## 9.7.3 Exploratory Analyses (If Applicable)

Not applicable.

## 9.7.4 Handling of Missing Data

The web questionnaire will be programmed in such a way that participants cannot skip questions. We thus do not expect missing values in submitted questionnaires, and neither replacement nor imputation of missing data is expected to be required. Since there is no applicable method unanimously accepted, there will be no replacement or imputation of missing data.

However, on the rare occasion that a system bug may occur and lead to a missing answer in a crucial screener question or a question that is part of the assessment of success, and it is

Template No.: RWI\_TP\_EPI0016 Revision 1 Reference: RWI\_WI\_EPI0005

Protocol/Study No: SC02 EMA/2018/19/PE

Page 47 of 92

not possible to obtain the missing answer through the quality control process as outlined in Section 9.8, the whole questionnaire will be dropped.

## 9.8 Quality Control

## 9.8.1 Data collection, validation and data quality control

Data will be collected using a web-administered questionnaire to physicians, pharmacists and patients. The survey will be conducted according to the SOPs of IQVIA Primary Intelligence and IQVIA Real World Evidence Solutions.

Data will be collected using an EDC system developed following a full validation process. A rigorous System Development Life Cycle that complies with IQVIA Primary Intelligence information technology SOPs is used for validation. The programmed survey will be tested and validated in accordance with IQVIA SOPs, which cover validation for all clinical and risk management-related applications. The internet-based repository will be used to store survey data and other relevant program information. Questions are programmed to ensure that they are asked in the appropriate sequence. Skip patterns are clearly indicated. Respondents cannot go back to a question once the question has been answered and cannot skip ahead without answering the previous question. Response options presented in a list are randomised to minimise positional bias. Programming will be reviewed by Quality Control and simulated users (User Testing) prior to implementation.

Collected data will be entered and stored in a database specific to the survey and the country. A study database will be created by merging of databases of each country. Prescribers, pharmacists and patients identifying information will be stored separately from survey data.

